9.5 STEPS TO DETERMINE IF AN ADVERSE EVENT REQUIRES EXPEDITED REPORTING

Step 1: Identify the type of adverse event using the NCI Common Terminology Criteria for Adverse Events (CTCAE v. 4.03).

Step 2: Grade the adverse event using the NCI CTCAE v. 4.03.

Step 3: Determine whether the adverse event is related to the protocol therapy Attribution categories are as follows:

- Definite – The AE *is clearly related* to the study treatment.
- Probable – The AE *is likely related* to the study treatment.
- Possible – The AE *may be related* to the study treatment.
- Unlikely – The AE *is unlikely related* to the study treatment.
- Unrelated – The AE *is clearly NOT related* to the study treatment.

Note: This includes all events that occur within 30 days of the last dose of protocol treatment. Any event that occurs more than 30 days after the last dose of treatment and is attributed (possibly, probably, or definitely) to the agent(s) must also be reported accordingly.

Step 4: Determine the prior experience of the adverse event.

Expected events are those that have been previously identified as resulting from administration of the agent. An adverse event is considered unexpected, for expedited reporting purposes only, when either the type of event or the severity of the event is not listed in:

- the current known adverse events listed in the Agent Information Section of this protocol;
- the drug package insert;
- the current Investigator's Brochure

10.0 SAFETY AND TOLERABILITY ASSESSMENTS

Safety will be monitored by assessing physical examinations, ECOG performance status, height and weight, vital signs, ECG, patient reported outcomes, laboratory assessments including hematology, chemistry, cholesterol and lipid panel, PT, INR, and urine as well as collecting adverse events at every visit. For details on AE collection and reporting, refer to Section 9.

10.1 PHYSICAL EXAMINATION, VITAL SIGNS, HEIGHT AND WEIGHT

A total body examination, vital signs, height and weight should be performed according to the visit schedule as outline in Table 7.1.

10.2 ECOG PERFORMANCE STATUS (PS)

The performance status will be assessed according to the ECOG performance status scale following the schedule in Table 7.1. See Appendix A.

10.3 LABORATORY ASSESSMENTS

Hematology, chemistry, coagulation, urinalysis, and cholesterol panels are to be performed according to the visit schedule outlined in Table 7.1 and 10.1.

Table: 10.1: Clinical Laboratory Parameters Collection Plan

Test Category	Test Name
Hematology	Hemoglobin, Platelets, white blood cells with differential (neutrophils, lymphocytes, basophils, eosinophils, monocytes)
Chemistry	Albumin, alkaline phosphatase, ALT, AST, creatinine, potassium, sodium, glucose, direct bilirubin,

	total bilirubin, total protein, magnesium, phosphorus
Cholesterol and Lipid Panel	Total cholesterol, LDL, HDL, triglycerides
Coagulation	PT, INR
Urinalysis	Glucose, protein, bilirubin, red blood cells, white blood cells, crystals, and bacteria.

11.0 CORRELATIVES STUDIES

Pathology Correlative Studies

A major obstacle to molecularly targeted chemotherapeutic agents has been obtaining relevant tumor tissue to measure the agents' biologic effects on target molecules or cellular pathways within the tumor. The utilization of sequential tumor biopsies to obtain tissue following treatment is well established in breast and colorectal carcinoma. (17) However, sequential tumor biopsies of liver tumors are less established due to a fear of procedural complications. The fear of bleeding events following liver biopsy of HCC appears unfounded and based on anecdotal evidence. A large, multi-institutional trial where patients with advanced chronic Hepatitis C underwent sequential liver biopsies demonstrated 16 cases (0.6%) of bleeding following 2740 liver biopsies. There were no deaths from peri-procedural bleeding and a platelet count under 60000 was identified as a risk factor. (18) Two large published series of core needle biopsy of HCC as a diagnostic measure report bleeding events in less than 1% of patients with no reported mortalities. In both series capsular location of HCC was associated with increased incidence of bleeding event. (19, 20) In this study all patients will potentially undergo up to two image-guided (either CT or Ultrasound) core needle biopsy of a single site of HCC at baseline (for clinical care) and between eight and nine weeks after the initiation of LEE011 (research only). The biopsy between eight and nine weeks following LEE011 initiation is not mandatory to initiate or continue with therapy and is subject to a separate informed consent. The baseline biopsy is needed to confirm HCC and RB positivity as an eligibility criterion. If archival formalin fixed paraffin embedded tissue is available for RB status analysis, a pre-treatment biopsy will not be required. To increase patient safety the following conditions must be met prior to liver biopsy:

- Platelet count $\geq 70,000$
- INR ≤ 1.8
- Target lesion not subcapsular in nature as determined by the participating interventional radiology team
- LEE011 will be discontinued for a period of 24-48 hours prior to biopsy

There is no evidence that an image-guided liver biopsy following TACE increases risk of bleeding or tumor seeding. Due to the consideration that TACE is not considered a curative procedure and viable tumor tissue remains after an initial biopsy it is anticipated that enough tumor tissue will be available for the planned studies. (21)

The patient will sign the informed consent for participation in research liver biopsy prior to the procedure. The liver biopsy will be performed by radiologists and the ancillary staff of Department of Radiology following the standard clinical protocol, which includes obtaining a separate informed consent for the procedure itself. The core samples will be provided to the Department of Pathology for histological and RB status confirmation in addition to the pathology laboratory. If a core biopsy is performed as a part of the patient's clinical care, extra cores will be obtained for surgical oncology laboratory, in addition to the cores necessary for clinical care. All cores will be obtained through the same needle to avoid the need of additional punctures and to minimize associated risks.

Tumor tissue will be used for several specific purposes. Pre-treatment biopsies will be used to evaluate potential markers of durable response, in addition to staining for p16ink4a and RB. This will include the analysis of phospho-RB, Cyclin D1, Cyclin E1, Cyclin E2, and p27Kip1 by immunohistochemistry. These proteins have been functionally associated with the response to CDK4/6 inhibitors. We will also assess baseline features of tumor proliferation by Ki67 and phospho-histone H3 staining and cleaved caspase 3 as a marker of tumor cell death. In parallel, if there is sufficient material we will employ RNA sequencing to delineate baseline features of tumor tissue. The molecular features of the tumor from RNA sequencing will be analyzed for association with PFS and other clinical features of disease to explore markers of response. We will use the post-treatment biopsies to determine the effect of LEE011 on tumor markers discussed above and by RNA sequencing. These studies will enable us to evaluate whether LEE011 is acting upon its targets in the tumor and to infer response markers with clinical outcome.

Plasma and serum samples (2 x 5 mL red tops and 2 x 6mL lavender tops) will also be collected at baseline and at the beginning of every cycle following initiation of LEE011. The blood samples will be used to measure circulating tumor DNA or other features of tumor burden that can be correlated with disease response. Storage and processing of the blood samples will be at the discretion of the pathology laboratory.

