1.5 PROLIFERATION FOLLOWING CHEMOEMBOLIZATION IN HEPATOCELLULAR CARCINOMA

There are multiple pre-clinical and clinical studies suggesting that hepatic artery embolization leads to increased HCC tumoral cell proliferation. Kim et al reported a case series in which explanted livers from transplanted patients undergoing chemoembolization 3 to 4 weeks prior to transplant had an elevated Ki67 proliferative index compared to non-treated controls. The increase in proliferative index within intratumoral endothelial and tumor cells was likely secondary to a post-embolization ischemic necrosis. (14) Farris et al also demonstrated a statistically significant difference in proliferation, again measured by the Ki67 proliferative index, between patients undergoing chemoembolization and control patients. (15)

1.6 CD4/6 INHIBITION AND REDUCTION OF PROLIFERATION IN PRE-CLINICAL HEPATOCELLULAR TUMOR MODELS AND EARLY STAGE CLINICAL TRIALS IN HCC

Our group previously demonstrated that inhibition of CDK4/CDK6 potently suppressed proliferation in HCC tumor models. For example, in a hepatoma xenograft model there was substantial suppression of proliferation following CDK4/6 inhibition (Figure 2). Similarly, in necrotic mouse livers following CCL4 administration, CDK4/6 inhibition had a profound impact on aberrant proliferation (Figure 3). These, and additional preclinical data served as the basis for a small single arm Phase II trial in advanced HCC using the CD4/6 inhibitor, palbociclib. This study used Rb and p16ink4 staining of tumor tissue as inclusion criteria. The immunohistochemical stains were developed and optimized by [name], who assisted in developing this study. This study treated 23 HCC patients who had failed on previous sorafenib therapy due to either intolerance or disease progression with palbociclib. The safety profile was largely consistent with CDK4/6 inhibition, the most common adverse event was bone marrow suppression. Grade 3 and 4 adverse events included the following: thrombocytopenia, 43%; neutropenia, 43%; leucopenia, 30%. (16) There was no evidence of liver related toxicity, including elevated AST and/or or AST and/or total bilirubin, following palbociclib administration in these patients with underlying cirrhosis. ([Littman](#) SJ, Gastrointestinal Cancers Symposium 2015, abstract 277)

[figure not shown]

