 - Physical examination
 - Comprehensive metabolic panel
 - Complete blood count without differential
 - Prothrombin time/INR

At this time the decision will be made to initiate LEE011 treatment.

LEE011 ADMINISTRATION WITH CHEMOEMBOLIZATION

Subjects are to be evaluated from toxicity with:

- Physical Examination (PE)
- Comprehensive Metabolic Panel (CMP)
- CBC
- ECG's

LEE011 will be initiated at the earliest of 7 days following embolization chemoembolization provided the following criteria are met:

- Serum bilirubin elevation $< 2.0 \times \text{ULN}$. If serum bilirubin $\geq 2.0 \times \text{ULN}$ then subjects will be assessed weekly and LEE011 will be initiated once bilirubin $< 2.0 \times \text{ULN}$.
- Resolution of Grade < 3 non-hematologic toxicity (other than bilirubin criteria above). If non-hematologic toxicity \geq Grade 3 then subjects will be assessed weekly and LEE011 will be initiated once $<$ Grade 2;
- Hematological toxicity of \leq Grade 2. If hematologic toxicity \geq Grade 3 then subjects will be assessed weekly and LEE011 will be initiated once \leq Grade 2.

If baseline AST, ALT and alkaline phosphate are elevated post chemoembolization decrease to baseline grade is necessary to continue/initiate LEE011;

- ECOG performance status ≤ 2 ;
- Serum AST, ALT, and/or Alkaline Phosphate $< 5 \times \text{ULN}$.

If criteria is not met, subjects will be reevaluated in 5-7 day intervals. If study subjects are unable to meet the above LEE011 starting criteria following initial chemoembolization treatment within 28 days after treatment, they will be removed from the study.

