3. In order for an accurate evaluation of baseline QTc, a total of three (triplicate) 12-lead ECGs will be performed after resting in a supine position for 5-10 min, with a 2 minute interval between each ECG (triplicate ECG's at screening only). Subsequent ECG's will be performed after resting in a supine position for 5-10 min, on Day 1, C1D15, and C2D15 of each treatment cycle (single ECG's)prior to chemoembolization and LEE011;

4. For all treatment visits there is a general +/- 3 day window on assessments to take into account scheduling over public holidays, if not specifically specified otherwise;
5. Baseline scans can be completed within 28 days prior to registration. After baseline, radiological assessments (CT –chest/abdomen/pelvis or MRI – abdomen/pelvis) must be performed as outline in Table 7.1 (Every 8 weeks during the treatment phase). CT Chest must be performed at baseline. CT Chest during treatment will be performed if clinically indicated. A visit window of +/- 7 days is allowed. Once the patient has been discontinued from the study and enters the efficacy phase, radiological assessments (CT or MRI) will continue on the every 8 weeks schedule until progression or for the first 12 months, whichever comes first. After a year, radiological (CT or MRI) assessments will be performed every 12 weeks until progression.
6. AE/Conmeds will be assessed from consent until up to 30 days last dose of LEE001 or until resolution, whichever comes first. Conmeds will recorded up to 30 day prior to consent;
7. The biopsy performed during screening is for HCC diagnosis and RB positive status and must be performed for the subject to be eligible for the study. However, initial TACE can be performed following agreement of informed consent while RB proficiency is being determined. If patient is not RB proficient patient will be removed from the study as a screen failed and offered other treatment. If the patient has archival formalin fixed paraffin embedded tissue no additional baseline biopsy will be done. The post treatment biopsy is optional and for research purposes only (phase 2 only). If the subject consented to the research biopsy during the consent process, it will be performed during the 8th and 9th week of after initiating treatment of LEE011 and at least one chemoembolization. NOTE: LEE011 should be held for 24-48 hours prior to and after the second biopsy. These held doses will not be made up and noted on the patient's diary.

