7.2.3 Patient Demographics and other Baseline Characteristics

The data that will be collected on patient characteristics at screening includes:

- Demographic (name, date of birth, age), sex, race/ethnicity;
- Diagnosis, RB status, and extent of cancer (staging) – tissue biopsy (required);
- Pertinent Medical History;
- Prior cancer treatment;
- All medications taken within 30 days before first treatment. If there are any changes, medications are to be updated on a continual basis.

Furthermore the following assessments will be performed:

- Vital Signs (BP, HR, T, RR);
- Adverse Events / Conmeds
- Height and Weight;
- Physical Examination (PE);
- ECOG Performance Status (PS);
- Laboratory Evaluations (chemistry, CBC, PT/INR, Lipid Panel, and UA)
- ECG (in Triplicate – baseline only)
- ECHO or MUGA;

- Radiological Assessments (RECIST 1.1) (CT - chest/abdomen/pelvis or MRI – abdomen/pelvis). Chest CT will be performed at baseline only. During the treatment phase, a Chest CT will be performed as clinically indicated;
- Pregnancy Test (Women of Child-bearing Potential Only).

7.2.4 **Pre-Treatment - Biomarker Tissue Biopsy (Required)**

After signing the treatment and biopsy informed consent, the screening biopsy, confirming HCC diagnosis, staging, and (RB+) result, must be complete within 28 days prior to registration unless the patient has archival formalin fixed paraffin embedded tissue to determine RB status. This biopsy is required to confirm patient eligibility. However, initial TACE procedure can be initiated prior to determination of RB status provided informed consent is signed and biopsy tissue is available for analysis.

7.2.5 **Biomarker / DNA Blood Collection (Optional – Phase II only)**

After signing the optional biomarker / DNA consent for future biomarker and DNA blood, samples will be collected at baseline, during treatment, and at the end of treatment or early-term visit. This procedure is for research and will not be used to make medical decisions regarding the patient's treatment.

7.3 **TREATMENT PHASE**

7.3.1 **Study Treatment**

Patients will be treated with chemoembolization once every 4 weeks (or every 28 Days), for a total of up to 4 chemoembolizations within the first 6 months.

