In addition, patients will be treated with 200, 400, or 600 mg LEE011 once daily by mouth (3 Weeks on / 1 Week off in a 28 day cycle) until disease progression, unacceptable toxicity, death, or discontinuation from the study treatment due to any other reason. For details of assessment, refer to Table 7.1.

7.3.2 **Post-Treatment – Biomarker Tissue Biopsy (Optional – Phase II only)**

The post treatment biopsy is optional and the patient must have consented to this second procedure during the initial consenting process. The second biopsy, for research purposes only, will be performed between Weeks 8 and 9 post initial treatment of LEE011. To qualify for the second biopsy, patients must have taken LEE011 for 21 consecutive days (21 days on treatment / 7 days off in a 28 day cycle) and had at least one chemoembolization.

7.3.3 **Additional Treatment Phase Assessments will be performed:**

- Vital Signs (BP, HR, T, RR);
- Adverse Events / Conmeds
- Weight;

- Physical Examination (PE);
- ECOG Performance Status (PS);
- Laboratory Evaluations (chemistry, CBC, PT/INR, and Lipid Panel);
- ECG;
- Radiological Assessments (RECIST 1.1) (CT - chest/abdomen/pelvis or MRI – abdomen/pelvis). During the treatment phase, a Chest CT will be performed as clinically indicated;

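### Section 11 reads the paired biopsy change as the effect of LEE011, but every pair also spans at least one TACE, so the change belongs to the combination

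*Combined protocol and SAP*

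**What the plan says.** Section 11 of the protocol gives the second biopsy a drug-specific purpose: "We will use the post-treatment biopsies to determine the effect of LEE011 on tumor markers discussed above and by RNA sequencing". It then draws a mechanistic conclusion: "These studies will enable us to evaluate whether LEE011 is acting upon its targets in the tumor". The markers named there are Ki67, phospho-histone H3, cleaved caspase 3, phospho-RB, cyclins D1, E1 and E2, and p27Kip1.

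The order of events is set elsewhere:

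- **Baseline tissue.** Section 7.2.4 states that the "initial TACE procedure can be initiated prior to determination of RB status provided informed consent is signed and biopsy tissue is available for analysis". Archival tissue may replace a fresh core (Section 11): "If archival formalin fixed paraffin embedded tissue is available for RB status analysis, a pre-treatment biopsy will not be required". Previous TACE is an exclusion (5.2.2).
- **LEE011 start.** Under LEE011 Administration With Chemoembolization (Section 6.12): "LEE011 will be initiated at the earliest of 7 days following embolization chemoembolization provided the following criteria are met".
- **Second biopsy.** Table 7.1, footnote 7: "it will be performed during the 8th and 9th week of after initiating treatment of LEE011 and at least one chemoembolization". Section 7.3.2 likewise requires that the patient has "had at least one chemoembolization". The biopsy is optional and limited to phase II.

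On what TACE does by itself, Section 1.5 cites studies suggesting that "hepatic artery embolization leads to increased HCC tumoral cell proliferation", measured by Ki67. Section 1.8 uses this as part of the rationale for the trial.

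**The concern.** Section 11 credits one component of a two-component treatment with a change measured across both. That would be harmless if TACE left the markers alone, but for proliferation the protocol argues the opposite. LEE011 is being tested partly because TACE is thought to provoke proliferation that a CDK4/6 inhibitor should suppress.

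At stake is the reading of the mechanistic work. If LEE011 suppresses the proliferation that TACE provokes, Ki67 at the second biopsy could sit near its baseline value. Someone following Section 11 could take that as absence of drug activity. Conversely, a marker that TACE moves could be credited to LEE011. Patients who agree to the second biopsy undergo an invasive research procedure for this answer, so its interpretation should be set out correctly beforehand.

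**Working it through.** **1. What each pair contains.**

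| | TACE exposure | LEE011 exposure | Source |
|---|---|---|---|
| Baseline tissue (fresh or archival) | none | none | 5.2.1, 5.2.2, 7.2.4, 11 |
| Second biopsy | at least one session | started 8 to 9 weeks earlier | Table 7.1 footnote 7, 7.3.2 |

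Write T for the mean marker change that TACE alone would produce by the second biopsy, and L for the further change due to LEE011. Apart from time and sampling differences, the mean paired change is T + L. All patients are treated in one arm (Section 12.1), with no biopsy between TACE and LEE011 and no TACE-only tissue. Nothing in the trial estimates T, so L cannot be recovered at any number of pairs.

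**2. What the documents say about T.** For Ki67, T is positive according to Sections 1.5 and 1.8, while the expected L is negative. If L = -T, the paired change is zero although the drug is active. One cited case series saw the Ki67 rise in livers explanted 3 to 4 weeks after TACE. No size is given. For the other listed markers no TACE effect is reported. Section 1.2 says TACE may cause tumour necrosis, which makes a change in cleaved caspase 3 plausible but does not document one.

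**3. Time from TACE to second biopsy.** LEE011 starts 7 to 28 days after the first TACE (Section 6.12). The 8th and 9th weeks of LEE011 cover about days 49 to 63.

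- Shortest interval: 7 + 49 = 56 days, or 8 weeks.
- Longest interval: 28 + 63 = 91 days, or 13 weeks.

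So the second biopsy falls about 8 to 13 weeks after the first TACE. With sessions every 4 weeks (7.3.1), at weeks 0, 4, 8 and 12, one to three and at the limit four sessions can precede it. The gap to the last session may then be short. Whether T persists at 8 to 13 weeks after a single session is not documented, and both TACE count and recency will differ between patients.

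**4. Planned analysis.** The plan gives no paired test, significance level, standard deviation or number of pairs, so there is no figure to reproduce. The only analysis named for the correlative studies is Cox regression of PFS on the parameters (Sections 3.1 and 12.1).

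**5. Illustration only.** Suppose someone ran a two-sided 5% paired t-test. Effects are in SDs of the within-patient change. The noncentral t distribution has n - 1 degrees of freedom and noncentrality (T + L) × √n. Every value of T, L and n is assumed.

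Chance of showing a decrease when L = -0.5:

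| T | n = 10 | n = 20 | n = 40 |
|---|---|---|---|
| 0 | 29% | 56% | 87% |
| +0.25 | 11% | 19% | 34% |
| +0.5 | 2.5% | 2.5% | 2.5% |

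Chance of declaring any change when L = 0:

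| T | n = 10 | n = 20 | n = 40 |
|---|---|---|---|
| 0.1 | 6% | 7% | 10% |
| 0.25 | 11% | 19% | 34% |
| 0.5 | 29% | 57% | 87% |
| 1.0 | 80% | 99% | about 100% |

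The result runs from negligible to complete depending on T, which the documents do not supply. Forty is the most pairs phase II could yield, and the optional biopsy will probably give fewer. More pairs do not remove the bias.

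**The case against.** The strongest reply is that little in the plan depends on this. The second biopsy is optional, for research only, and drives no dose, eligibility, stopping or efficacy decision. That stands, and it is why the point is minor.

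Three further objections limit how far the point goes:

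- **No test is written.** A reader might infer that the plan contains a paired test with an inflated error rate, or a rule by which an unchanged Ki67 means no target engagement. Neither exists. The rates above describe a natural comparison under assumed inputs and are not properties of the plan. Nor can one contrast them with the power available against a TACE-only reference, because that would treat a quantity this trial never measures as known without error.
- **The TACE effect is documented for proliferation only.** A reader might infer that all markers will move because of TACE. The documents report no TACE effect on phospho-RB, the cyclins or p27Kip1, the pathway proteins closest to the drug's action. Even for Ki67, persistence to the second biopsy is unknown after a single TACE, and repeat TACE is given only if indicated (6.12.7).
- **Objective 2.2.3 is not at fault.** A reader might infer that this secondary objective is mis-stated too. It speaks of treatment response, and Section 6.2 defines study treatment as the combination, so it already fits what the biopsies can show.

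None of this rescues the two sentences in Section 11. Their attribution to LEE011 is unsupported whatever test is used, and for markers with no reported TACE effect the lack of a report is not evidence that the effect is zero.

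**Conclusion.** The point holds for Section 11 only. The paired change estimates the net change after TACE plus LEE011, and the design offers no means of isolating the LEE011 part. This follows from the order of events and the single arm, and needs no numerical assumption. The direction of the likely error is documented for Ki67 alone, where a TACE-induced rise could mask a real LEE011 effect. Its size cannot be stated, because the documents give neither the magnitude of the TACE shift nor its persistence to 8 to 13 weeks.

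Severity is minor. The objective is exploratory, and the MTD, PFS and OS are untouched. The documents do not support a claim that the plan will reject wrongly at some stated rate.

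**What to change.** Change Section 11 only; 2.2.3 needs no change.

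1. Replace the two LEE011-specific sentences with a statement that the second biopsies describe the change in tumour markers, and in RNA sequencing, from baseline after TACE plus LEE011, and that this change cannot be attributed to LEE011 alone.
2. State that an unchanged Ki67 is not evidence against LEE011 activity, since the protocol's rationale expects TACE to raise it.
3. Report paired changes descriptively, showing for each pair the number of TACE sessions and the days since the last TACE at biopsy. Separate archival from fresh baseline tissue, because no limit on the age of archival tissue is stated.

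The cost is a few sentences and one descriptive table or listing based on procedure and biopsy dates. No extra biopsy, patient or change in treatment is needed. The downsides are a weaker mechanistic claim and small cells. A listing by patient may serve better than subgroup summaries, and neither will identify a LEE011 effect.
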